6.7. NA Re-treatment Criteria and Monitoring After Stopping of NA

After completing treatment with JNJ-3989, JNJ-6379 (or their matching placebos) and NA at Week 48 (or after premature discontinuation), participants will be monitored closely during the follow-up phase.

After stopping NA treatment, participants should be monitored as follows:

- Regular monitoring visits will be every 4 weeks during the follow-up phase in accordance with the [Schedule of Activities](#).
- A post-treatment HBV DNA value of >20,000 IU/mL should trigger re-testing of ALT/AST, HBV DNA, and total and direct bilirubin within a maximum of 7 days from receipt of the data and further repeats as necessary (ie, weekly until HBV DNA returns to <20,000 IU/mL).
- A post-treatment HBV DNA value of >2,000 IU/mL (but <20,000 IU/mL) should trigger a re-test within 14 days from receipt of the data and further repeats as necessary (ie, every other week until HBV DNA returns to <2,000 IU/mL).
- A post-treatment ALT value of >5x ULN should trigger re-testing of ALT, AST, alkaline phosphatase (ALP), total and direct bilirubin, INR, albumin, and HBV DNA on a weekly basis until ALT and AST levels have returned to <5x ULN.

After stopping NA treatment, participants should restart NA treatment:

- Immediately with signs of decreasing liver function based on laboratory findings (eg, INR, direct bilirubin) or clinical assessment (eg, ascites, hepatic encephalopathy).
- Immediately with an HBV DNA value of >100,000 IU/mL (irrespective of confirmation and/or ALT increase).
- With confirmed post-treatment HBeAg seroreversion (HBeAg positive after it was negative at NA completion).
- With confirmed* post-treatment increases in HBV DNA >2,000 IU/mL and ALT >5x ULN.
- With confirmed* post-treatment increases in HBV DNA >20,000 IU/mL.

*At least 4 weeks apart frequency of visits as described above.

Note: Additional re-testing and/or earlier restarting of NA treatment is at the investigator's discretion, even if the above cut-offs are not yet met.

To avoid delays in decision making, sites are encouraged to run local re-testing in parallel with central re-testing in the situations described above that require more frequent re-testing. Local test results are to be collected in the CRF and/or source documents, including information on the HBV DNA assay used. In addition, to avoid delays in NA re-treatment, it should be considered to dispense NA to participants who potentially met the NA re-treatment criteria (eg, pending confirmation) and who will not be available to come to the study site immediately at the time the confirmatory test results will become available. This should ensure that the participant can immediately re-start NA treatment if indicated, upon direct confirmation by the investigator.

Management of intervention-emergent ALT/AST elevations is discussed in Section [8.3.6.3](#), Intervention-emergent ALT/AST Elevations.

NA re-treatment criteria and monitoring after stopping of NA are presented graphically in Section [10.13](#), Appendix 13.

6.8. Intervention After the End of the Study

Refer to Section 6.7 of the Master Protocol PLATFORMPAHPB2001.

The investigator should consider to re-start NA treatment per local standard of care at the EOS visit (Follow-up Week 48) for participants who discontinued NA treatment at Week 48, who did not re-start NA treatment during the follow-up phase, and who did not achieve and maintain HBsAg seroclearance. NA will not be provided by the sponsor after the final study visit.

7. DISCONTINUATION OF STUDY INTERVENTION AND PARTICIPANT DISCONTINUATION/WITHDRAWAL

If a participant discontinues study intervention for any reason before Week 48, the participant will have an early withdrawal visit and will enter follow-up unless he/she withdraws consent. If the reason for withdrawal from the study is withdrawal of consent, then the participant will be offered an optional safety follow-up visit. Study intervention assigned to the participant who discontinued study intervention may not be assigned to another participant.

7.1. Discontinuation of Study Intervention

JNJ-3989 and JNJ-6379 (or matching placebos) must be discontinued before Week 48 for all reasons listed in Section 7.1 of the Master Protocol PLATFORMPAHPB2001 and for all additional intervention-specific reasons. All the discontinuation criteria are listed below and the intervention-specific criteria are highlighted (colored fill). For the few criteria from the Master Protocol that are specified or more restricted in this ISA, the changes compared to the Master Protocol are also highlighted (colored fill). When JNJ-3989 or JNJ-6379 (or the matching placebos) are discontinued, NA treatment may be continued or, in consultation with the sponsor, discontinued based on investigator judgement.

The discontinuation criteria are:

- The investigator believes that for safety or tolerability reasons (eg, AE) it is in the best interest of the participant to discontinue JNJ-3989 and JNJ-6379 (or matching placebos).
- The participant becomes pregnant.
- The participant has a \geq grade 3 rash or allergic reaction.
- The participant has signs of hepatic decompensation (ie, clinical evidence of ascites, bleeding varices, or hepatic encephalopathy).
- The participant has a confirmed \geq grade 3 estimated glomerular filtration rate (eGFR) abnormality and a drop from baseline of >10 mL/min/1.73 m², considered at least possibly related to JNJ-3989 or JNJ-6379. Change of NA treatment should be considered according to the prescribing information.
- The participant has a QTcF prolongation (defined as a QTcF value of >500 ms, or an increase from baseline of >60 ms) at any given time point.
- The participant requires ≥ 7 days of treatment with any of the disallowed medications listed in Section 6.5 and does not intend to discontinue treatment with the disallowed medication.

- The participant has confirmed HBV virologic breakthrough (ie, confirmed on-treatment HBV DNA increase by $>1 \log_{10}$ IU/mL from nadir or confirmed on-treatment HBV DNA level >200 IU/mL in participants who had HBV DNA level $<\text{LLOQ}$ of the HBV DNA assay). In case of virologic breakthrough, the investigator in consultation with the sponsor should consider changing the NA (to an NA that is not cross-resistant to the current NA, after evaluation of all data available). In case of virologic breakthrough, the same assessments will be done at an unscheduled visit as will be done in case of an ALT flare, but no PBMC sample will be taken (see Section 8.3.6.3 and [Schedule of Activities](#)).
- The participant has ALT/AST elevations, as described in Section 8.3.6.3, Intervention-emergent ALT/AST Elevations.

Note: The grades are based on the DAIDS Toxicity Grading Scale (see Section 10.9, Appendix 9, DAIDS Table).

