8.3.6.1. Rash

Participants should be informed that they should contact their doctor immediately when they notice any generalized skin reaction. This skin reaction should be evaluated in the clinic the same day (if possible) or the next day.

All rash events should be captured in the AE section of the CRF. A separate Rash page will be completed in case of a rash event.

Monitoring of the evolution of rash events will be performed as described in Table 5 in Section 10.5, Appendix 5, Rash Management.

When safety blood samples are drawn as per the rash management guidelines, these should be processed by the local laboratory. The following parameters will need to be tested: AST, ALT, sedimentation rate, complete blood cell count (including hemoglobin, hematocrit, red blood cell [RBC] count, white blood cell [WBC] count, differential count [neutrophils, lymphocytes, monocytes, eosinophils, and basophils], and platelet count), and creatinine. The values of the local laboratory assessments need to be transcribed in the CRF by the study site personnel.

The participant may be treated symptomatically until the rash resolves. Oral antihistamines (eg, cetirizine, levocetirizine) and/or topical corticosteroids may provide symptomatic relief but effectiveness of these measures has not been established. If systemic corticosteroids exceeding 5 mg of prednisolone equivalent/day are required for treatment of rash, JNJ-3989 and JNJ-6379 (or placebos) need to be permanently discontinued. NAs can be continued. If the rash is considered to be most likely due to concomitant illness or non-study drugs, standard management, including discontinuation of the likely causative agent, should be undertaken.

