8.3.6.2. Acute Systemic Allergic Reactions

Grade 1 (Localized Urticaria [Wheals] With no Medical Intervention Indicated)

Participants may continue the intake of study interventions.

Cetirizine, levocetirizine, topical corticosteroids or antipruritic agents may be prescribed.

Participants should be advised to contact the investigator immediately if there is any worsening of the acute systemic allergic reaction.

Grade 2 (Localized Urticaria With Intervention Indicated, or Mild Angioedema With no Intervention Indicated)

Participants may continue the intake of study interventions.

Cetirizine, levocetirizine, topical corticosteroids or antipruritic agents may be prescribed.

Participants should be advised to contact the investigator immediately if there is any worsening of the acute systemic allergic reaction, in which case the participant will permanently discontinue the intake of JNJ-3989 and JNJ-6379 (or placebos). Rechallenge is not allowed. The participant's NA treatment may be discontinued based on investigator judgement in consultation with the sponsor.

Grade 3 (Generalized Urticaria, Angioedema With Intervention Indicated, or Symptoms of Mild Bronchospasm) and Grade 4 (Acute Anaphylaxis, Life-threatening Bronchospasm, or Laryngeal Edema)

Participants will permanently discontinue the intake of JNJ-3989 and JNJ-6379 (or placebos). Rechallenge is not allowed. The participant's NA treatment may be discontinued based on investigator judgement in consultation with the sponsor.

Participants will be treated as clinically appropriate. Participants should be followed until resolution of the AE and standard management should be undertaken.

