			clinical stability is reached. Safety laboratory assessments are required on Day 1 and are required thereafter only if the previous values were abnormal (but may be performed at the investigator's discretion). If the rash progresses to a higher grade, safety laboratory assessments of the higher grade should be followed. Digital pictures ^c of skin lesions may be taken at the investigator's discretion.	
Grade 3 rash^b	Vesiculation, moist desquamation, or ulceration OR Any cutaneous event with 1 of the following: - Elevations in AST/ALT >2×baseline value - Fever >38°C or 100°F - Eosinophils >1.00×10 ³ /µL - Serum sickness-like reaction	Must permanently discontinue JNJ-3989 and JNJ-6379 (or placebos); no rechallenge allowed NA treatment may be discontinued based on investigator judgement in consultation with the sponsor	Day 0: required on-site visit. Safety laboratory assessments required to be performed. Digital pictures ^c of skin lesions may be taken at the investigator's discretion (recommended). Determine if participant was adhering to the recommended sun-protective measures. If appropriate, provide sun protection counseling. Day 1: required on-site visit. Safety laboratory assessments required to be performed. Digital pictures ^c of skin lesions may be taken at the investigator's discretion (recommended). Further visit(s): appropriate follow-up required until resolution of rash or until clinical stability is reached. Safety laboratory assessments and photography (digital pictures ^c of skin lesions) are recommended to be performed until the rash severity resolves to grade 2 or grade 1.	Required ^d Biopsy not required, but may be performed at the dermatologist's discretion.

Table 5: Management of Rash Events by Severity Grade

	Definition	Study Intervention Action	Activities by Day^a	Referral to Dermatologist and Dermatology Activities

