Alopecia (scalp only)	Detectable by participant, representative, or physician AND Causing no or minimal interference with usual social & functional activities	Obvious on visual inspection AND Causing greater than minimal interference with usual social & functional activities	NAP	NAP
Bruising	Localized to 1 area	Localized to more than 1 area	Generalized	NAP
Cellulitis	NAP	Nonparenteral treatment indicated (eg, oral antibiotics, antifungals, antivirals)	IV treatment indicated (eg, IV antibiotics, antifungals, antivirals)	Life threatening consequences (eg, sepsis, tissue necrosis)
Hyperpigmentation	Slight or localized causing no or minimal interference with usual social & functional activities	Marked or generalized causing greater than minimal interference with usual social & functional activities	NAP	NAP
Hypopigmentation	Slight or localized causing no or minimal interference with usual social & functional activities	Marked or generalized causing greater than minimal interference with usual social & functional activities	NAP	NAP
Petechiae	Localized to 1 area	Localized to more than 1 area	Generalized	NAP
Pruritus^c (without skin lesions)	Itching causing no or minimal interference with usual social & functional activities	Itching causing greater than minimal interference with usual social & functional activities	Itching causing inability to perform usual social & functional activities	NAP
Rash Specify type, if applicable	Localized rash	Diffuse rash OR Target lesions	Diffuse rash AND Vesicles or limited number of bullae OR superficial ulcerations of mucous membrane limited to 1 site	Extensive or generalized bullous lesions OR Ulceration of mucous membrane involving 2 or more distinct mucosal sites OR Stevens Johnson syndrome OR Toxic epidermal necrolysis

IV: intravenous; NAP: not applicable

^c For pruritus associated with injections or infusions, refer to the [SITE REACTIONS TO INJECTIONS AND INFUSIONS](#) section.

ENDOCRINE AND METABOLIC				
PARAMETER	GRADE 1 MILD	GRADE 2 MODERATE	GRADE 3 SEVERE	GRADE 4 POTENTIALLY LIFE- THREATENING
Diabetes Mellitus	Controlled without medication	Controlled with medication OR Modification of current medication regimen	Uncontrolled despite treatment modification OR Hospitalization for immediate glucose control indicated	Life threatening consequences (eg, ketoacidosis, hyperosmolar nonketotic coma, end organ failure)

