5.2.2. Main Estimand for the Primary Endpoint

Study Objective: To evaluate the efficacy of the study intervention 24 weeks off-treatment.

Scientific Question: in HBeAg negative, virologically suppressed adult population with chronic HBV infection, what is the benefit of JNJ-3989 200 mg+JNJ-6379+NA (Arm 1) for 48 weeks in terms of functional cure 24 weeks after stopping all study interventions compared with NA alone (Arm 2)?

A) Study Intervention:

- Arm 1: JNJ-3989 (200 mg) + JNJ-6379 (250 mg qd) + NA
- Arm 2: Placebo + Placebo + NA

B) Study Population: HBeAg-negative chronic HBV-infected patients who are virologically suppressed by being treated with NA.

C) Variable: Response status defined as participants who meet the criteria defining functional cure at Week 72 (responders) as in Section 5.2.1

D) Intercurrent events:

- Treatment discontinuation prior to Week 48: if the participant discontinued treatment prior to Week 48 then s/he will be considered non-responder (composite strategy).
- Major protocol deviations affecting efficacy: [Attachment 1](#) identifies the deviations considered intercurrent event. Participants with such deviations and who have missing data for the endpoint will be considered as non-responders (composite strategy). For all other deviations not considered intercurrent events, the data are used regardless of the occurrence of major protocol deviations (treatment policy strategy).
- Deaths prior to Week 72 are handled in a composite strategy as participants who die prior to Week 72 will be considered as non-responders.
- NA re-treatment between Week 48 and 72: the participant will be counted as non-responder (composite strategy).

E) Population-level summary: Difference in proportion of participants with functional cure status at Week 72 between study intervention arms.**5.2.2.1. Main Estimator****5.2.2.1.1. Analysis Methods**

The main estimator is constructed using a Mantel-Haenszel ([Mantel N., et al. 1959](#)) test controlling for stratification factors, i.e., screening HBsAg level ($<1,000$ IU/mL or $\geq 1,000$ IU/mL), race (Asian versus non-Asian) and type of NA (TDF/TAF versus ETV) for the difference in proportions between the intervention arms (Arm 1 minus Arm 2). A 2 sided 90% CI of the difference in proportions will be provided.

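### Protocol 7.1 claims a complete, DAIDS-graded list of stopping criteria, but Appendix 5 and Sections 8.3.6.1 and 8.3.6.2 require permanent stops that 7.1 neither lists nor points to

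*Protocol*

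**What the plan says.** Section 7.1 of the protocol introduces its list with "All the discontinuation criteria are listed below and the intervention-specific criteria are highlighted (colored fill" and closes it with "Note: The grades are based on the DAIDS Toxicity Grading Scale". For skin and allergy the list has one entry: a rash or allergic reaction of grade 3 or higher. A separate entry covers disallowed medication. It applies only when at least 7 days of treatment are needed and the participant "does not intend to discontinue treatment with the disallowed medication". Section 7.1 sends the reader to 8.3.6.3 for ALT/AST elevations. It does not refer to 8.3.6.1, 8.3.6.2 or Appendix 5.

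Four other places bear on the same events:

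- **Appendix 9 (DAIDS), rash row.** Grade 1 is a localized rash. Grade 3 is a diffuse rash with vesicles or a few bullae, or "superficial ulcerations of mucous membrane limited to 1 site".
- **Appendix 5, Table 5.** Grade 3 has a second limb, "Any cutaneous event with 1 of the following": AST/ALT above 2 times baseline, fever, eosinophils above 1.00×10³/µL, or a serum sickness-like reaction. The action is a mandatory permanent stop of both agents, without rechallenge.
- **Section 8.3.6.1.** "If systemic corticosteroids exceeding 5 mg of prednisolone equivalent/day are required for treatment of rash", both agents are to be stopped permanently. No minimum duration is given.
- **Section 8.3.6.2.** After a grade 2 reaction, the participant is told to report any worsening, "in which case the participant will permanently discontinue the intake of JNJ-3989 and JNJ-6379 (or placebos".

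On the endpoint, the protocol (9.4.1.1) counts withdrawal from treatment before Week 48 as non-response. The SAP (5.2.2, item D) agrees: "if the participant discontinued treatment prior to Week 48 then s/he will be considered non-responder".

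**The concern.** A list of mandatory stopping criteria that calls itself complete will be used as the reference when a site decides whether a participant must come off the investigational agents. If it omits mandatory stops, or grades the same rash on another scale, two sites can treat the same event differently and each can cite the protocol.

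The first thing at stake is safety: a site using 7.1 alone is not obliged to stop agents that Appendix 5 or 8.3.6 says must be stopped. The second is consistency of the primary endpoint, because an early treatment stop is itself an outcome under the composite strategy.

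**Working it through.** **Step 1. Same event, two pages.**

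| Event | Section 7.1 (DAIDS grades) | Other page |
|---|---|---|
| Localized rash with fever, or AST/ALT >2× baseline, or eosinophils >1.00×10³/µL | DAIDS grade 1; no stop required | Table 5 grade 3; permanent stop required |
| Rash needing a short course of systemic steroid above 5 mg/day prednisolone equivalent | Disallowed drug (Table 3), but a stop is required only at 7 days or more with no intention to stop the drug | 8.3.6.1: permanent stop, any duration |
| Grade 2 allergic reaction that worsens but stays grade 2 | Below grade 3; no stop required | 8.3.6.2: permanent stop |
| Allergic reaction of grade 3 or 4 | Stop | 8.3.6.2: stop (no conflict) |

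The first row is the main conflict. The DAIDS rash row has no fever, transaminase or eosinophil limb, so the two scales give different grades to one event. The same mismatch appears inside 8.3.6: its opening text refers to DAIDS for rash, and 8.3.6.1 then directs sites to Table 5. No order of precedence is stated.

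**Step 2. The fever entry.** Table 5 gives 38°C and 100°F as if they were one threshold. (100 − 32)/1.8 = 37.8°C, whereas 38 × 1.8 + 32 = 100.4°F, which is the pairing in the Appendix 9 fever row. The two figures differ by 0.2°C.

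**Step 3. Route to the primary endpoint.** Inputs: 80 and 40 participants, 5% control response and a 20-point difference, so 25% in Arm 1 (protocol 9.2).

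- One would-be responder turned into a non-responder moves the observed rate by 1/80 = 1.25 points in Arm 1 or 1/40 = 2.5 points in Arm 2.
- Most participants are not would-be responders. At the design rates, and if stops are unrelated to response, the expected shift per discordant stop is 0.25 × 1.25 = 0.31 points in Arm 1 and 0.05 × 2.5 = 0.125 points in Arm 2.

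**Step 4. Scale against the plan's power.** The plan states more than 91%.

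- Pooled normal formula, one-sided 0.05: mean rate = (80 × 0.25 + 40 × 0.05)/120 = 0.183; null SE = √(0.183 × 0.817 × (1/80 + 1/40)) = 0.0749; alternative SE = √(0.25 × 0.75/80 + 0.05 × 0.95/40) = 0.0594; z = (0.20 − 1.645 × 0.0749)/0.0594 = 1.29. Power is 90.2%.
- Exact enumeration of the unstratified Mantel-Haenszel test gives 91.7%, which reproduces the stated figure.

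The documents give no frequency for discordant stops. The following range is an assumption: a share s of Arm 1 is stopped under the wider rules, none in control, independently of response, so the Arm 1 rate becomes 0.25 × (1 − s).

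| s | 0% | 1.25% | 2.5% | 5% | 10% |
|---|---|---|---|---|---|
| Exact power | 91.7% | 91.1% | 90.4% | 88.9% | 85.3% |

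**The case against.** The strongest reply is that 7.1 is incomplete rather than contradicted. A reader might infer that it tells a site to keep the participant on treatment when another page says stop. It does not. It lists conditions that require a stop and never instructs continuation, and its first bullet lets the investigator stop the agents for any safety or tolerability reason. A site that follows Table 5 or 8.3.6 therefore does not breach 7.1, and a site managing a rash is sent to Table 5 by 8.3.6.1.

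The steroid rules can also be read as general and specific. The 7-day rule covers any disallowed drug, and the amendment history gives its purpose as preventing accidental intake from forcing a stop. The allergy gap is thin: the 8.3.6.2 grade definitions match DAIDS and grades 3 and 4 agree with 7.1. The fever discrepancy is editorial.

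Most of this stands. The steroid and allergy rules are extra conditions missing from the list, not opposite instructions. What remains is that permission to stop does not reproduce a mandatory stop, that 7.1 says its list is complete, and that it names DAIDS as the scale while Table 5 uses another. Its cross-reference to 8.3.6.3 alone makes the omission of the other sections easy to miss.

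**Conclusion.** The concern holds as an internal inconsistency that should be fixed. The rash-grade mismatch is the substantive part, the unlisted steroid and allergy stops are secondary, and the fever entry is minor. The safety argument needs no frequency: required stops are absent from a list presented as complete.

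The effect on the primary result is probably small. Even the assumed 5% of Arm 1 with none in control lowers power from 91.7% to 88.9%. Two stronger readings are tempting but unsupported:

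- **That every discordant stop shifts the primary rate.** Only a would-be responder does; anyone else is a non-responder either way.
- **That stopping the two agents is automatically non-response.** Protocol 9.4.1.1 and SAP 5.2.2 speak of treatment, and the SAP's definition of study treatment (Section 2) includes the NA. The rash and allergy rules allow the NA to continue. Neither document says whether stopping JNJ-3989 and JNJ-6379 alone counts, so non-response in that case is a likely reading rather than a stated one.

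The Master Protocol was not available, but this protocol says its own Section 7.1 lists all the criteria.

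**What to change.** - Reconcile 7.1 with Appendix 5, 8.3.6.1 and 8.3.6.2 so that each event has one rule. The sponsor's clinical team chooses the rule; nothing here favours one.
- Name in 7.1 the scale that decides a rash stop.
- List the steroid and allergy stops in 7.1 or cross-refer to them. Otherwise remove the sentence claiming that the list is complete.
- Put a single fever figure in Table 5.
- State in the SAP whether stopping only JNJ-3989 and JNJ-6379 while the NA continues is treatment discontinuation for the primary estimand.

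The cost is amendment wording and one SAP sentence, with no extra visits or participants. A new CRF field is not essential: discontinuation reasons are already summarized by arm and treatment (SAP 4.1), rash has its own CRF page (protocol 8.3.6.1), and adverse events leading to discontinuation are tabulated and listed (SAP 6.1.2).
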